5.5. Prior and Concomitant Procedures

Prior and concomitant procedures will be coded using Medical Dictionary for Regulatory Activities (MedDRA) version 23.0 or higher.

Prior procedures are defined as procedures with a start date prior to the first dose of vibegron on study URO-901-3005 or URO-901-3006. Concomitant procedures will be defined as procedures started on or after the first dose of vibegron but prior to the last dose + 5 days, or started prior to the first dose of vibegron and were ongoing during the study. Post procedures are defined as any procedure initiated after last dose of vibegron + 5 days (See Table 2). Partial procedure start dates will be imputed as detailed in 4.2.3.

All procedures will be listed for the SAF-Ext population, sorted by treatment, subject number, start date, SOC and PT, with indicators of prior and concomitant status.

5.6. Prior and Concomitant Medication

Prior and concomitant medications will be coded using the World Health Organization (WHO) Drug B3-Sept Format, 2020 version or later. Except for Prior OAB medication, the number and percentage of subjects taking prior medications and concomitant medications will be summarized overall by ATC (Anatomical Therapeutic Chemical) Levels 2 and 4 for all subjects in the SAF-Ext. Prior OAB medications will be summarized by ATC Levels 2, 4 and Preferred Term in the SAF-Ext. Prior medications, OAB medication and concomitant medications will be listed for all subjects in the SAF-Ext.

5.6.1. Prior Medication

Prior medications are defined as those medications taken prior to the first dose of vibegron on study URO-901-3005 or URO-901-3006. The prior non-OAB and prior OAB medications will be summarized separately.

The following criterion will be used for selecting prior OAB medication:

Table 7. OAB Medication Selection

Class	Variable Selected	Selection
Anticholinergics	Preferred Term	darifenacin, fesoterodine, fesoterodine fumarate hyoscyamine, oxybutynin, oxybutynin hydrochloride, propantheline, solifenacin, solifenacin succinate, tolterodine, tolterodine l-tartrate, trospium, trospium chloride
Beta-3 adrenergic agonists	Preferred Term	mirabegron, vibegron

Combination medications will be identified if the preferred term contains a term from the selection.

5.6.2. Concomitant Medication

Concomitant medications are defined as medications that were started on or after the first dose of vibegron on study URO-901-3005 or URO-901-3006 but prior to the last dose of vibegron + 5 days or started prior to the first dose of vibegron and were ongoing or ended after the first dose of vibegron. Partial medication start dates will be imputed as detailed in 4.2.3.

Non-OAB and OAB concomitant medications will be summarized separately.

6. EFFICACY ANALYSIS

Subjects were asked to fill out a Bladder Diary for 3 consecutive days prior to the Run-in visit, Baseline visit, Weeks 2, 4, 8, 12, 16, 20, 24, 28, 36, and 52.

In general, the FAS-Ext will be used for all analyses of non-incontinence efficacy endpoints. The FAS-Ext-I will be used for all incontinence efficacy endpoints; these are the endpoints related to UUI episodes and total incontinence episodes.

6.1. Secondary Efficacy Analysis

The secondary efficacy analysis will be done on the FAS-Ext or FAS-Ext-I population, repeated in a supportive analysis on the PP-Ext or PP-Ext-I population, respectively. Descriptive

summaries for observed and CFB for each efficacy endpoint will be provided by visit and treatment group.

For the assessment of change from baseline to Week 52 for endpoints with repeated-measures over time, a mixed model for repeated measures (MMRM) analysis incorporating on-treatment values at all time points for the subjects in the 52-week treatment group will be used. The model takes into account correlation within the same subject over time by using all available data on the subjects within the same covariate set. With the assumption of missing at random (MAR), this approach will provide unbiased estimates of treatment effects.

The MMRM model will include terms for visit, baseline value, alpha blocker use with or without 5-ARI (with vs. without), baseline urinary incontinence (yes vs. no) [for the FAS-Ext and PP-Ext analyses only], region (US vs. non-US), and any other parameter-specific covariates noted in sections 6.1.1 and 6.1.2. The Kenward-Roger adjustment will be used with restricted (or residual) maximum likelihood (REML) to make statistical inference. An unstructured covariance matrix will be used to model the correlation among repeated measurements. If the unstructured covariance model fails to converge with the default Newton-Raphson algorithm, the Fisher scoring algorithm will be used to provide initial values of the covariance parameters. In the rare event that none of the above methods yield convergence, the following structures will be investigated: heterogeneous Toeplitz, Toeplitz, heterogeneous First-Order Autoregressive [AR (1)], heterogeneous compound symmetry (HCS), and compound symmetry (CS). The covariance structure converging to the best fit, as determined by Akaike's information criterion (AIC), will be used.

Estimates of least square means (LSMEANS), standard errors, and 95% confidence intervals will be presented at each time point. The estimated LSMEANS (Standard Error (SE)) of CFB over time from the model will be plotted.

An example of the SAS code for the base procedure is given below:

```
proc mixed data = datain method = reml;  
  class AVISITN USUBJID ARI UI REGION;  
  model CHG = AVISITN ARI UI REGION BASE  
    / ddfm=KR solution chisq;  
  repeated AVISITN / subject=USUBJID type=UN r rcorr;  
  lsmeans AVISITN / cl alpha=0.05;  
run;
```

Where AVISITN is the visit number, USUBJID is the unique subject identifier, ARI indicates if the subject used alpha blocker with or without 5-ARI at baseline (with or without), UI indicates baseline urinary incontinence (yes or no), REGION indicates if the subject is in the United States or in the non-US countries and BASE indicates baseline value. The default Newton-Raphson algorithm is employed for type = UN.

The normality assumptions for the primary analysis model will be assessed by inspection of the residuals from the model and normal probability plots. If assumptions of normality are not met, additional supportive analysis of the data will be performed in order to assess the robustness of the conclusions drawn from the model.

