9.4. Statistical Analyses

9.4.1. Statistical Methods for Efficacy Analysis

Statistical analysis of efficacy endpoints will be for descriptive purposes only. Baseline will be defined as the baseline from the Study URO-901-3005. Further inclusion of data from URO-901-3005 in the reporting of this study will be described in the SAP.

For the analysis of continuous change from baseline endpoints (eg, change from baseline in average number of micturitions, change from baseline in the average number of urgency episodes, change from baseline in average number of nocturia episodes, change from baseline in daily urge urinary incontinence episodes, change from baseline in average IPSS Storage score, and change from baseline in average volume voided per micturitions), a mixed model for repeated measure (MMRM) with restricted maximum likelihood estimation will be used. This model corrects for dropout and accounts for the fact that measurements taken on the same subject over time tend to be correlated, by using all available information on subjects within the same covariate set to derive an estimate of the treatment effect for a dropout-free population.

The analysis model for each efficacy endpoint will include terms for visit, baseline, stratification factors (only those that were statistically significant in URO-901-3005 will be included in the models), and baseline score. Only subjects on active treatment in both URO-901-3005 and URO-901-3006 will be included in the model. Adjusted means and 95% confidence intervals will be presented for each visit.

An unstructured covariance matrix will be used to model the correlation among repeated measurements. The Kenward-Roger adjustment will be used with restricted (or residual maximum likelihood (REML) to make proper statistical inference. If the unstructured covariance model fails to converge with the default Newton-Raphson algorithm, the Fisher scoring algorithm or other appropriate methods can be used to provide initial values of the covariance parameters. In the rare event that none of the above methods yield convergence, a structured covariance will be used to model the correlation among repeated measurements.

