1.2.4. Sample Size Justification

Approximately 300 subjects rolling over from Study URO-901-3005, in addition to other long-term safety data with vibegron, is sufficient to characterize the long-term safety profile of vibegron 75 mg once daily in men with symptoms of OAB on stable doses of pharmacological therapy for BPH. With the assumption of approximately 33% dropout, 100 subjects will be expected to complete the study for the duration of 1-year on vibegron.

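### The MMRM uses one baseline slope for every visit, so the Week 52 mean can be biased under MAR if dropout depends on baseline and that slope differs between visits

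*SAP*

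**What the plan says.** Protocol 9.4.1 states: "The analysis model for each efficacy endpoint will include terms for visit, baseline, stratification factors". It names no interaction. SAP 6.1 likewise lists visit and baseline value as separate terms, and its SAS code agrees: "model CHG = AVISITN ARI UI REGION BASE".

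The covariance is flexible: "An unstructured covariance matrix will be used to model the correlation among repeated measurements". The mean model is not, because a single coefficient for BASE applies from the first post-baseline visit to Week 52. That first visit is Week 2 for the diary endpoints and Week 4 for IPSS storage.

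On missing data, SAP 6.1 says: "With the assumption of missing at random (MAR), this approach will provide unbiased estimates of treatment effects". The only model check planned there concerns normality of residuals.

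The reported quantity is the adjusted mean at each visit, from "lsmeans AVISITN / cl alpha=0.05", with no AT option. Only men in the 52-week group enter the model, so there is no treatment contrast. On retention, SAP 1.2.4 plans "With the assumption of approximately 33% dropout". Protocol 9.4.1 describes the efficacy analysis as descriptive.

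**The concern.** The dependent variable is change from baseline, so its slope on baseline depends on how strongly each visit's value is related to the baseline value. That relation may not be the same after 2 weeks as after 52. If the slope does change, the common slope is a compromise across visits and does not fit Week 52. If the men still present at Week 52 also differ in baseline from those who left, the adjustment to the overall mean baseline is off by the slope error times that baseline difference. MAR does not prevent this, because the fault lies in the mean model.

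At stake is the headline number for each of the six secondary endpoints, the Week 52 adjusted mean. With one group in the model, an error cannot cancel between arms.

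**Working it through.** **The plan's own figure.** SAP 1.2.4 expects 100 men to complete a year on vibegron. The documents give no allocation ratio. If half of the 300 were randomized to vibegron, 150 × (1 − 0.33) = 100.5, which reproduces it. So 150 men in the model is an assumption.

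**Assumed inputs (not in the documents).** Baseline SD 3.0 and residual SD 2.5 micturitions per day; true Week 52 change −2.5; ten post-baseline visits. Dropout falls after Week 28 and depends on baseline only, so the data are MAR. Every man who drops out lacks Week 52, and half of them also lack Week 36. The log-odds of dropout per baseline SD are 0, 0.5 or 1.0. Both models were fitted by maximum likelihood with unstructured covariance to 60,000 simulated men. LS means were taken at the subject-level mean baseline.

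**Week 52 bias, common slope (episodes per day).**

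| True slope, Week 2 to Week 52 | Dropout unrelated to baseline | 10%, baseline-dependent | 33%, baseline-dependent |
|---|---|---|---|
| −0.5 throughout | about 0 | 0.001 to 0.005 | 0.000 to 0.006 |
| −0.3, levelling at −0.5 by Week 12 | about 0 | 0.002 to 0.008 | 0.024 to 0.025 |
| −0.3 to −0.6 | about 0 | 0.015 to 0.033 | 0.055 to 0.093 |
| −0.2 to −0.7 | about 0 | 0.023 to 0.046 | 0.073 to 0.134 |

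With a slope per visit, the bias lay between −0.009 and 0.012 in every cell, which is simulation noise.

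**Hand check.** If earlier visits lent no information, the bias would be (slope at Week 52 − common slope) × (completers' mean baseline − overall mean baseline). Take slopes −0.3 to −0.6, 33% dropout and log-odds 1.0. The raw observed mean was off by 0.489, so the baseline difference is 0.489 / (−0.6) = −0.815. The fitted common slope was −0.439. The product is (−0.6 + 0.439) × (−0.815) = 0.13, against 0.093 simulated. The gap is what the correlated earlier visits recover. For slopes −0.2 to −0.7 the difference is 0.571 / (−0.7) = −0.816, giving (−0.7 + 0.432) × (−0.816) = 0.22, against 0.134 simulated. Other simulations of the same design gave up to about 0.2, near this limit.

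**Relative to the standard error.** In 150 replicates of 150 men at 33% dropout, the standard error was 0.230 to 0.245 for the SAP model and 0.243 to 0.250 with the interaction. The Monte Carlo error of each mean bias is about 0.02. Approximate 95% interval coverage at bias-to-SE ratio r is Φ(1.96 − r) − Φ(−1.96 − r):

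- Slopes −0.3 to −0.6: 0.092 / 0.238 = 0.39, coverage about 93%.
- Slopes −0.2 to −0.7: 0.142 / 0.245 = 0.58, coverage about 91%.
- A bias of 0.19: 0.19 / 0.245 = 0.78, coverage about 88%.

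**LSMEANS at the record-level mean.** By default BASE is set to its average over analysed records, and men who stay supply more records. Take 33% dropout and log-odds 1.0.

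- Dropouts' mean baseline exceeds the overall mean by 0.815 × 0.67 / 0.33 = 1.65.
- Missing records per man: 0.33 + 0.165 = 0.495, leaving 10 − 0.495 = 9.505.
- Record-level minus subject-level mean: −0.495 × 1.65 / 9.505 = −0.086.
- Times the slope: 0.04 at −0.44, 0.05 at −0.6, 0.06 at −0.7.

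At log-odds 0.5, the observed mean was off by 0.289. The baseline difference is then 0.289 / (−0.6) = −0.48, the dropouts' excess is 0.98, and the shift at slope −0.44 is about 0.02. This effect does not need the slope to change.

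**The case against.** A reader might infer that dropout related to baseline is enough to bias the Week 52 mean, or that the bias is predictable because correlation with baseline must fall over a year. The documents support neither. Baseline is in the model, so with a constant slope the modelled mean stays unbiased even at 33% strongly baseline-dependent dropout. No section reports a slope or correlation by visit.

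Other points on the plan's side also stand:

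- The 33% is a planning figure, not the missing rate at Week 52 within the analysis set. FAS-Ext requires an evaluable diary measurement in the extension, so men who leave before one are not in the model. For IPSS, the Week 52 window opens after Day 309 and the early-withdrawal visit includes the questionnaire, so some withdrawals still supply a value.
- Only micturitions were computed; the other five endpoints are covered by the same reasoning, not by numbers.
- The SAP model already does most of the work. At 33% baseline-dependent dropout the raw observed means were off by 0.24 to 0.57.
- The analysis is descriptive, tests no hypothesis, and follows the protocol. Omitting the interaction is a modelling choice, not a contradiction.

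These points limit the size and weight of the concern. They do not rescue the statement that MAR alone gives unbiased estimates, because the plan neither states nor checks that the slope is constant.

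**Conclusion.** The concern holds conditionally. The Week 52 adjusted mean can be biased under MAR if dropout depends on baseline and the baseline slope also differs between visits; if either fails, the slope-related bias is about 0. Under the assumed values with slopes still changing up to Week 52, it is roughly 0.02 to 0.05 micturitions per day at 10% dropout. At 33% baseline-dependent dropout it runs from about 0.02, where the slope levels off early, to about 0.2, where it changes steeply. The top of that range is about 0.8 standard errors with 150 men.

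The record-level baseline mean is a separate effect, which needs only baseline-dependent dropout. In these scenarios, where men with higher baselines leave more often, both effects have the same sign and understate improvement. This is worth correcting because the remedy is nearly free, not because any conclusion of the study is threatened.

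**What to change.** - Add BASE*AVISITN to the model text and the MODEL statement in SAP 6.1 for all six secondary endpoints.
- Add AT BASE=value to the LSMEANS statement, with the value set to the subject-level mean baseline of the 52-week group in the relevant analysis set.
- Reword the missing-data sentence so that unbiasedness holds under MAR and a correctly specified mean model.

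The interaction costs one parameter fewer than the number of visits. That is five for IPSS storage (six visits). It is eight or nine for diary endpoints, because SAP 6.1.1 lists nine visits while SAP 6 also includes Week 20; the two lists should be aligned. The loss of precision is slight at most in the simulations. It was not examined in the smaller FAS-Ext-I, so precision and convergence should be watched there. No new data are needed.

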2.2. Background

2.3. Overactive Bladder in Men with Benign Prostatic Hyperplasia

OAB is highly prevalent and affects approximately 16% of the population in the United States and Europe. Prevalence increases with age, affecting approximately one third of people 75 years and older [Stewart, 2003; Milsom, 2001]. Despite similar prevalence between the sexes and growing clinical trial evidence that men benefit from pharmacotherapy, men are less likely to use treatment for OAB [Goldman, 2016].

The International Continence Society (ICS) defines OAB as urgency, with or without urge incontinence, usually associated with frequency and nocturia [Abrams, 2002]. Urgency is defined as a sudden compelling desire to void which is difficult to defer and, from the medical definition perspective, it is a necessary symptom for OAB. Urgency incontinence is the involuntary loss of urine accompanied by urgency (referred to as OAB Wet) and is present in approximately one-third of patients with OAB [Stewart, 2003; Milsom, 2001]. In the absence of incontinence, OAB is referred to as OAB Dry. Urgency incontinence is distinguished from stress urinary incontinence, which is the involuntary loss of urine on effort or physical exertion (eg, sporting activities), or upon sneezing or coughing. When both components are present, the classification is mixed urinary incontinence, with either urgency or stress specified as the predominant component.

Although the overall prevalence of OAB in men and women is similar, there are major differences in predominating symptoms. Men are more likely to experience urgency, frequency, and nocturia accompanied by lower urinary tract symptoms (LUTS) associated with voiding dysfunction, whereas women are twice as likely to experience incontinence [Tubaro, 2017]. Since most men with OAB symptoms do not have urinary incontinence, the micturition frequency and the urgency become the predominant symptoms that characterize the disease for

the men with OAB on pharmacological therapy for BPH [Helfand, 2012]. Among men, urinary incontinence significantly increases after the age of 65 years.

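### The single-arm MMRM reports LS means weighted equally over the levels of its class covariates, not to the mix of men analysed, and the SAP does not say which is meant

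*SAP*

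**What the plan says.** SAP 6.1 describes an MMRM "analysis incorporating on-treatment values at all time points for the subjects in the 52-week treatment group will be used". The sample code declares "class AVISITN USUBJID ARI UI REGION" and fits "model CHG = AVISITN ARI UI REGION BASE". This is a main-effects model with no treatment term and no interactions, and baseline is continuous. The incontinence term is included "for the FAS-Ext and PP-Ext analyses only", so the urge urinary incontinence (UUI) model lacks it. SAP 6.1.1 adds a further two-level factor to the urgency model: at most 12 versus more than 12 micturitions per day.

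The estimate is requested by "lsmeans AVISITN / cl alpha=0.05", with no OM, AT or other weighting option. On reporting, the text says "Estimates of least square means (LSMEANS), standard errors, and 95% confidence intervals will be presented at each time point". It does not say which population the adjusted mean refers to. The code is introduced with "An example of the SAS code for the base procedure is given below", but nothing else in the SAP sets the weights.

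**The concern.** By default, PROC MIXED averages an LS mean equally over the levels of every class factor that is not in the LSMEANS effect. In a two-arm additive model this rarely matters, because the same weights enter both arms and drop out of the difference. This model has one arm. The LS mean and its 95% CI are what the MMRM tables and figures report, with Week 52 presented first.

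The default therefore fixes the population being described: one that is half 5-ARI users, half incontinent and half US, whatever the men in the analysis look like. Protocol 9.4.1 says the model is there to correct for dropout, so a reader who sees a gap between the adjusted and the raw mean will put it down to dropout. Equal weighting can add a second gap that has nothing to do with dropout, and the report would not let the reader separate the two.

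**Working it through.** **The plan's own figure.** The documents state no LS-mean weights, factor splits or factor effects, so there is no figure to reproduce on this point.

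**What the code computes.** With each factor coded 0/1 and b the effect of its level 1 on change:

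LS mean at a visit = visit term + 0.5·b(ARI) + 0.5·b(UI) + 0.5·b(REGION) + slope × mean baseline.

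Weighted to the sample, each 0.5 becomes p, the observed share at level 1. Hence

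equal-weight minus observed-margin LS mean = Σ b × (0.5 − p).

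Here b is the difference in *change* between levels, given baseline and the other factors. With no visit-by-factor interaction, the shift is the same constant at every visit. Baseline is held at its mean, so it does not contribute.

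**Which factors enter, by endpoint.**

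| Endpoint | Factors averaged equally |
|---|---|
| Micturitions, nocturia, IPSS storage, volume voided | 5-ARI, incontinence, region |
| UUI | 5-ARI, region |
| Urgency | 5-ARI, incontinence, region, ≤12 vs >12 micturitions |

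**What is known of the shares.** Protocol 2.3 describes urgency incontinence as "present in approximately one-third of patients with OAB", a figure for OAB patients of both sexes, and adds that most men with OAB symptoms are continent. This is background and suggests a share under one half. The documents give no split for 5-ARI use or region.

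**Illustration, incontinence alone** (micturitions/day). The shares of 0.20 and 0.33 and the effects of 0.5 and 1.0 are assumptions; only the one-third has any basis in the documents.

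| Share incontinent | b = 0.5 | b = 1.0 |
|---|---|---|
| 0.20 | 0.30 × 0.5 = 0.15 | 0.30 × 1.0 = 0.30 |
| 0.33 | 0.17 × 0.5 = 0.085 | 0.17 × 1.0 = 0.17 |
| 0.50 | 0 | 0 |

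**Illustration, three factors**, assumed shares 0.20, 1/3 and 0.75, each effect 0.5 in size:

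- All effects of the same sign: 0.150 + 0.083 − 0.125 = 0.108.
- Third sign reversed: 0.150 + 0.083 + 0.125 = 0.358.

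Factors can therefore offset or reinforce one another.

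**Simulated check.** The settings were 150 subjects, nine visits, SD 2.5, within-subject correlation 0.6, 33% monotone dropout and 400 runs per setting, with effects of 0.5.

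| Shares | Shift by formula | Simulated shift | SE, equal ÷ observed margins |
|---|---|---|---|
| 0.5 / 0.5 / 0.5, same sign | 0 | −0.002 | 1.01 |
| 0.20 / 0.33 / 0.75, same sign | 0.108 | 0.116 | 1.27 |
| 0.20 / 0.33 / 0.75, third reversed | 0.358 | 0.376 | 1.27 |
| 0.20 / 0.20 / 0.20, same sign | 0.45 | 0.431 | 1.42 |

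The SE ratio did not change when an effect changed sign. The loss of precision comes from the splits, so it can occur even where the factors barely predict change.

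**Scale.** The planned 100 one-year completers follow from 300 × 0.5 × (1 − 0.33) = 100.5, if half came from the vibegron arm (assumed). With an assumed SD of 2–3 micturitions/day, a simple 95% half-width is 1.96 × 2/√100 = 0.39 to 1.96 × 3/√100 = 0.59. The illustrated incontinence shift is smaller than that, but it is systematic.

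**The case against.** The strongest reply is that little depends on this number. Efficacy is descriptive, there are no formal hypotheses, and SAP 6.1 also plans raw observed and change summaries by visit. SAP 5.2 tabulates incontinence, 5-ARI use and region for the efficacy sets, so the actual mix will be visible. The shift is constant over visits, so whether the response holds from Week 24 to Week 52 is untouched. Equal weighting is a recognised convention, and the code is only an example.

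Much of this stands, and it limits the consequences to the level of the adjusted mean and the width of its interval. It does not remove the point. The adjusted mean is a reported result in its own right, and description is its whole purpose. The tables are specified to show LS means, SEs and CIs, not factor coefficients, so a reader who knows the mix still cannot re-weight. The example code is also the only place where the weights are determined.

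The reply is right on size as well. The 20% share and the 0.5–1.0 effect come from no passage, and the shift needs an effect on change after adjusting for baseline, which the documents do not supply.

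**Conclusion.** The point holds as a gap in specification that is cheap to close. As coded, the LS means refer to an equal-weight covariate mix that the SAP neither states nor justifies. Protocol 2.3 suggests that mix is not the enrolled one for incontinence. For that factor the illustrative shift is 0.09–0.30 micturitions/day under the assumed shares and effects, and zero with an even split or no effect on change. The CI is wider when splits are unequal.

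A reader might infer four stronger things that the documents do not support:

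- That all six endpoints are averaged over the same three factors. Only four are; UUI has two and urgency has four.
- That the 5-ARI and region splits are known to be uneven. They are not given.
- That the time course or a test is distorted. The shift is constant across visits, and there is no test.
- That observed-margin weights would make the LS mean equal the raw Week 52 mean. The two can still differ, because the MMRM uses all available visits under missing at random while the raw mean uses only men observed at Week 52.

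**What to change.** Use `lsmeans AVISITN / om=margins cl alpha=0.05;`, where `margins` (a name chosen here) holds every analysed 52-week subject once at every visit in that model, with all model covariates. One record per subject would not do, because it would not carry all levels of the AVISITN class effect. OM taken from the analysis data itself would give more weight to men with more visits. The balanced dataset avoids both problems.

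Add one sentence to SAP 6.1: LS means are weighted to the observed covariate mix of the analysed 52-week subjects. If equal weights are really intended, say so and print the factor splits beside the LS means.

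The cost is one extra derived dataset, built to match each model's analysis set and visit schedule, and one sentence. No data collection changes.
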